
we will recruit additional participants from the academic institutions affiliated with each participating VA, namely University of California, San Diego (UCSD) and Oregon Health & Science University (OHSU), where Drs. [name] and [name] have joint appointments, respectively. UCSD programs that can refer participants include Senior Behavioral Health and the Memory and Resilience Center (see letter of support from [name], Medical Director and Co-Director of these two outpatient programs). At UCSD, the Senior Behavioral Health Program and the Memory, Aging, and Resilience Center evaluate and treat about 75 patients per year with MCI. OHSU programs that can refer participants include the National Institute on Aging (NIA)-funded Layton Aging & Alzheimer's Disease Center (Directed by Co-Investigator [name]) and the OHSU Division of General Internal Medicine and Geriatrics (Directed by Co-Investigator [name]) (see letters of support from Drs. [name] and [name]). At OHSU, the Layton Center longitudinally follows about 450 research volunteers at risk for MCI or dementia, and enrolls 60 new volunteers per year.

Retention and reimbursement. We had a relatively low non-completer rate (11%) among subjects enrolled in our funded CCT study with OEF/OIF Veterans with mild TBI; moreover, all of the non-completers dropped out prior to the start of the group, while those who attended the first session of the group completed the 10-week CCT intervention. The five ME-CCT for MCI groups that we have run at VAPORHCS have had a similar drop-out rate of ~10%. We have, therefore, conservatively assumed a 20% drop-out rate and will recruit 216 participants to yield a final sample size of 180. Our power analyses were calculated assuming 20% attrition, yielding a total final sample of n=180 (see power analyses for each hypothesis). We will use subject compensation and reminder phone calls to reduce our attrition rate. Participants will be compensated \$50 after each of the first three assessments, and \$75 after the fourth and final follow-up assessment. If participants complete all four assessments, their total compensation will be \$225. VASDHS participants who elect to use the Fitbit during the study will be able to keep the Fitbit device at the conclusion of their study participation.

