Experimental intervention (ME-CCT). ME-CCT was developed, authored, and piloted by the PIs, Drs. [name] and [name] (see **Pilot Study 1**). ME-CCT is a manualized group-based behavioral intervention (8 weeks, 2 hours per week, 16 hours total) designed to improve cognitive and everyday functioning in patients with MCI. See **Table 2** for a description of the ME-CCT intervention and **Appendix 6** for the treatment manual.

Control intervention (SC). We propose to use a robust control condition, Goal-focused Supportive Contact (SC), a group therapy intervention that provides the same frequency and amount of therapist and other group member contact as ME-CCT, but does not provide training in cognitive strategies, lifestyle strategies, or motivational enhancement. The SC intervention will have a primary focus on setting and achieving short or long-term goals. Focusing on goals is intended to provide "face validity" to potential participants and to enhance treatment attendance and reduce drop-out in this population. Sessions will be semi-structured and consist of check-in about the week prior, current symptoms or concerns, followed by a flexible discussion about setting and working toward goals. Sessions will typically include components of empathy and non-directive reinforcement of health, coping, and symptom management behaviors that grow out of group discussions, with only minimal therapist guidance. Participants will be asked to think about how the discussions had bearing on their individual goals, and will be encouraged to ask for the advice of other participants in achieving specific goals, but no specific training will be provided. Study therapists will not provide advice on reaching goals, but will encourage feedback from other group members. The SC control condition is being used in one of [name] currently-funded cognitive training studies (NIMH R34) and has been used in published studies by her colleague, [name] [6, 7].

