Procedures. Potential subjects will be identified through the specific recruitment methods described in the below section 11. Prior to enrollment, interested Veterans will be **pre-screened**. Study personnel will conduct a medical record review, including neuropsychological assessment records, to ensure study eligibility. As described in the following sections related to recruitment (Section 9: "Recruitment and Feasibility" and Section 11: "Recruitment"), study personnel will then contact individuals by phone or letter, depending on the specific recruitment method, to answer questions about the study, confirm interest in participation, and to schedule an initial study visit. All eligible participants will then complete an **initial study visit** which will include **informed consent** and **baseline measures** (see **Table 5**); all participants will be carefully screened to ensure their ability to comprehend study procedures, risks and benefits. Participants at the VASDHS site will be offered the opportunity to use a Fitbit to track their physical activity and sleep during the study. (The Fitbit Charge 2 is a non-invasive, water-resistant, wrist-worn device that measures steps taken, distance traveled, heart rate, and sleep quality and stages.) Upon enrollment, we will create a unique login ID and password for each participant to enable us to track their data on the Fitbit website each week of the 8-week intervention; we will upload these data during the weekly group session. When connected to a compatible device (i.e., study computer), data are automatically uploaded to the users' Fitbit accounts. The researchers will bring a study laptop to the groups each week, at which time the researchers will upload participants' data for adherence and assessment purposes. These data will then be "dumped" into and stored on a secure study server. We will also upload their data during their last assessment at 21 weeks; however, participants will be given the option of coming to the VA between the 8 week and 21 week assessment to upload their data so they can get continued summary of their progress each week. The participants will be allowed to keep the device when the study ends and guided through the procedure for establishing a new username and password, thereby terminating the research staff's access to their account. All eligible participants will then be **randomized** to either the ME-CCT or SC group. Randomization tables will be prepared by [name], the study statistician, at the beginning of the study. For each site, groups will be randomly assigned to ME-CCT or SC based on the site's randomization table. New study participants will be allocated to the current group awaiting randomization. Once group membership reaches the minimum of 6, the group will be randomized by [name], who will be blind to membership of each group. Randomization procedures and enrollment for each site will be monitored by [name], and if imbalance occurs at any site, he will recommend the necessary adjustment. Following randomization, participants will receive the **intervention (ME-CCT or SC)** for 8 weeks. To reduce the risk of treatment

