Assessment Methodology. Participants will complete the assessment battery at weeks 0, 4, 8 and 21, consisting of self-report questionnaires and performance-based tests of cognition and functioning. Performance-based tests will not be administered at week 4, however, to avoid practice effects. Collateral informants (e.g., spouse, adult child, relative), when available, will complete questionnaires at weeks 0, 4, 8, and 21. Study measures and the rationale for including them are listed in **Table 5**. Measures will take < 3.5 hours to complete at week 0 (baseline), < 1 hour at week 5, and approximately 3 hours at weeks 8 and 21 (follow up). We have selected measures based on 4 criteria: 1) importance for assessing constructs evaluated in our aims, 2) brevity (to reduce subject burden), 3) reliability, and 4) demonstrated validity. The rationale for including each study measure is listed in **Table 5** and further described below. Data collected at the second site, VAPORHCS, will be transferred to VASDHS via drive behind the VA firewall, as we have done in a previous study. Fitbit data will be collected at the VASDHS site only.

Fitbit Charge 2 (<https://www.fitbit.com/charge2>): This non-invasive, water resistant device, which is worn around the wrist, will be used to measure participants' activity levels, heart rate, and sleep quality. The Fitbit uses a three-dimensional accelerometer to sense movement. It measures steps taken, distance walked, calories burned, active/inactive minutes, stationary time, heart rate, hours and quality of sleep, as well as stages of sleep. The Fitbit's measurement of self-paced and prescribed intensity exercise has been validated against the Omron HJ-720IT accelerometer and direct observation.

Table 5. Study Measures

Measure	Purpose /Specific Aim: Hypothesis	Construct Assessed	Weeks Administered	Time (min)
Patient Health Questionnaire-9 (PHQ-9) [74].	Subject characterization; Exploratory Aim 4.	Depression symptom severity.	0	2
General Anxiety Disorder-7 Scale (GAD-7) [75].	Subject characterization; Exploratory Aim 4.	Anxiety symptom severity.	0	2
PTSD Checklist (PCL)	Subject characterization; Exploratory Aim 4.	PTSD symptom severity.	0	2
Wide Range Achievement Test-4-Reading (WRAT-4) [76].	Subject characterization; Exploratory Aim 4.	Reading ability (premorbid IQ estimate).	0	5

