improvements in objective cognitive performance and functional capacity. The frequency with which participants use these strategies will be evaluated with the Portland Cognitive Strategies Scale (PCSS) [69]. Our pilot data demonstrate significant increases in cognitive strategy use on the PCSS in Veterans with MCI following ME-CCT (see **Pilot Study 1**). We also found significantly increased strategy use on the PCSS in combat Veterans following CCT for TBI (see **Pilot Study 2**). Using the CHAMPS Physical Activity Questionnaire, the Fitbit data, and the Cognitive Activity Inventory, we will also evaluate whether increases in physical activity and mental activity mediate improvements in objective cognitive performance and functional capacity.

Baseline Characterization and Moderators (Exploratory Analyses). Baseline measures were selected to ensure that baseline rates of demographics, medical conditions, BMI, medication and substance use, psychiatric disorders, premorbid IQ, and significant other involvement are equivalent across groups. If between group analyses reveal any differences across groups in terms of these factors, they will be controlled for in subsequent analyses. In order to preliminarily explore for whom this intervention is most effective, we will evaluate whether these baseline variables (see **Table 5**) or baseline performance on primary and secondary endpoint measures moderate ME-CCT associated improvements in objective cognitive performance and functional capacity.

HYPOTHESIS-SPECIFIC DATA ANALYSIS PLAN AND POWER ANALYSES

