16a2) See Privacy and Data Security Plan for further details.

Yes No

16b) Is SSN used for any purpose other than scanning Consent/HIPAA into the medical record? (e.g., subject payments, use of clinical record)

Yes No

16b2) If YES, indicate purpose and justification:

SSN is needed for subject payments and last 4 digits are needed to ensure access only to appropriate patients in CPRS.

Section 16.1 Entry of CPRS Notes

16.1) Entry of a CPRS Research Informed Consent Note is required if any of the following apply:

- The subject is admitted as an inpatient or treated as an outpatient for research
- The study involves research medical care or may affect medical care.
- The Informed Consent and HIPAA Authorization indicate notes will be entered

Notes: Scanning the Consent and HIPAA Authorization into CPRS is no longer required. Linking the Consent to the Research Informed Consent Note is permitted (Unless the study has a Certificate of Confidentiality) and may be especially useful for trials involving the Research Pharmacy. For Non-Veterans, if Research Informed Consent Notes are entered then the NOPP Acknowledgement must be scanned in. A Research Progress Note should also be entered for each procedure or intervention. Address the CPRS note requirement:

16.1a) Is entry of CPRS notes required based on the above criteria?

Yes No

16.1b) Are CPRS notes entered?

Yes No

16.1c) Is a CPRS waiver is requested instead?

Yes No

Section 17 - Potential Benefits

17) Discuss benefits that may be gained by the subject as well as potential benefits to society in general. (see ? for guidance)

This research may provide participants with information about their psychological and cognitive functioning. Participants may experience a reduction in their complaints regarding cognitive impairment and may experience an improvement in their cognitive ability, usage of cognitive strategies, self-efficacy, adaptive functioning, and ability to reliably manage personal affairs. They will receive information about their activity levels and sleep that they may find helpful. The knowledge gained from this study could lead to effective treatments that otherwise might not have been made available. Additionally, study results will help expand knowledge of treatments appropriate for Veterans with Mild Cognitive Impairment.

Section 18 - Risk/Benefit Ratio

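### The exploratory Fitbit mediator is meant to capture an increase in physical activity, but no pre-intervention Fitbit period is designated

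*Combined protocol and SAP*

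**What the plan says.** Section 9, Procedures: "Participants at the VASDHS site will be offered the opportunity to use a Fitbit to track their physical activity and sleep during the study". No arm is excluded, and in the order of the text the offer precedes randomisation. Under Assessment Methodology, "Fitbit data will be collected at the VASDHS site only". Under Retention and reimbursement, use is elective ("VASDHS participants who elect to use the Fitbit during the study"), and no uptake figure is given.

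Staff will "track their data on the Fitbit website each week of the 8-week intervention", with uploads made at the weekly group sessions for adherence and assessment. A further upload is planned at week 21. Between weeks 8 and 21, wearers may come in to "upload their data so they can get continued summary of their progress each week". Section 9.9 repeats this schedule. Section 17 lists the information as a benefit: "They will receive information about their activity levels and sleep that they may find helpful".

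Under Mediators (Exploratory Analyses), with CHAMPS, the Fitbit and the Cognitive Activity Inventory as sources, "we will also evaluate whether increases in physical activity and mental activity mediate improvements in objective cognitive performance and functional capacity". The Exploratory Analyses part of the data analysis plan names the Fitbit again. Table 5 schedules CHAMPS and the Cognitive Activity Inventory at weeks 0, 4, 8 and 21. It has no Fitbit row, and no Fitbit summary variable is defined elsewhere.

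H3 tests CHAMPS and the Cognitive Activity Inventory with the H1 model, which includes site and site-by-treatment terms but none for Fitbit use.

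**The concern.** A mediator defined as an increase needs a starting value. The planned Fitbit record starts with the intervention, so the analysis would have to use activity levels during treatment.

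Randomisation supports comparing those levels between arms. It does not protect the other half of a mediation analysis, the link from mediator to outcome within an arm. People who were already active before enrolment may do better or worse on cognition and functional capacity for reasons unrelated to any change in activity. Without a baseline reading, that long-standing association is counted as evidence of mechanism. At stake is a claim that objectively measured activity carries part of the ME-CCT effect. The confirmatory tests are not at stake.

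**Working it through.** **1. Which activity measures have a starting value**

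| Source | Before the intervention | During | Week 21 |
|---|---|---|---|
| CHAMPS | week 0 | weeks 4, 8 | yes |
| Cognitive Activity Inventory | week 0 | weeks 4, 8 | yes |
| Fitbit | none designated | weekly for 8 weeks | yes |

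Only the Fitbit lacks one.

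**2. Effect on the mediator-outcome link.** Within an arm, let A0 be activity before the intervention, A1 activity on treatment and Y the outcome given its own baseline, all in SD units. Let r be the correlation of A0 with A1, and let Y = b·A1 + c·A0 + error. A model without A0 estimates b + r·c, so the error is r·c. The plan gives no r for the Fitbit. Borrowing the repeated-measures correlations from its H1 power analysis:

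- r = .2: error .2c
- r = .45: error .45c
- r = .5: error .5c
- r = .8: error .8c

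If the arms differ in activity by the plan's medium effect of .5 SD, the mediated effect is misstated by .5 × r × c, which is .1c to .4c. The documents do not give c; if it is zero, there is no bias.

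**3. Which form of baseline use removes it.** With A0 in the model, the coefficient on A1, or on the change A1 − A0, is b. A raw change score without A0 is less safe. Assuming equal SDs, Cov(A0, A1 − A0) = r − 1 and Var(A1 − A0) = 2(1 − r), so the slope of A0 on change is −1/2. The estimate becomes b − (b + c)/2 = (b − c)/2.

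**4. Size of the Fitbit analysis.** The plan gives no power for mediation. For its H3 figure of 80% (.5 SD, two-sided alpha .01, 180 analysed, 90 per arm), power = Φ(.5·√(90/2) − 2.576) = Φ(.778) = 78.2%, which reproduces it closely. San Diego is half the sample, so 180/2 = 90 participants, or 45 per arm with even attrition. For an arm difference of .5 SD in Fitbit activity at two-sided .05, with uptake assumed:

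- full uptake (45 per arm): Φ(2.372 − 1.960) = 66%
- half uptake (22.5 per arm): Φ(1.677 − 1.960) = 39%
- with a baseline covariate at r = .45, the residual SD is √(1 − .45²) = .893, giving 76% and 47%

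These figures ignore clustering by therapy group, so they are on the optimistic side. A baseline therefore also helps precision.

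**5. H3.** Let u be uptake, and e1 and e0 the effect of wearing the device on CHAMPS in ME-CCT and SC. The pooled contrast shifts by .5 × u × (e1 − e0), where .5 is San Diego's share. The shift is zero if e1 = e0, positive if the device helps more in ME-CCT, and negative if it helps more in SC. The documents give none of u, e1 or e0, so no figure is put in.

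**The case against.** The analysis is exploratory, and the plan calls it preliminary. CHAMPS has a week-0 value, so physical activity can be studied as a mediator without the Fitbit. Randomisation protects the arm comparison of on-treatment Fitbit levels. All of this stands, and it limits the point to one mediator without removing the confounding in step 2.

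A reader might infer that a Fitbit increase cannot be computed at all. The documents do not support that. The device is offered around the initial visit, and a group waits for at least 6 members before it is randomised, so some wear before session 1 may exist. Change from the first weeks could also be estimated, although those weeks are already on treatment. What is missing is a designated window and a rule for using it.

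A reader might also infer that the device contaminates the control arm and dilutes H3. SC "does not provide training in cognitive strategies, lifestyle strategies, or motivational enhancement", and the word continued in the description of the optional visits, together with Section 17, suggests that wearers receive summaries. But the only summaries tied to a stated occasion belong to the optional visits after week 8, session uploads are described as serving adherence and assessment, and a tracker is not clearly lifestyle training. Both San Diego arms are offered the device, so an equal effect cancels and an unequal one could enlarge the contrast as easily as shrink it. The planned site-by-treatment term might flag a difference, though it cannot separate the device from other site differences.

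**Conclusion.** The point holds for the Fitbit mediator in Exploratory Aim 4. As written, it has no designated pre-intervention value, and its association with outcome is open to confounding of size r × c. The range .2c to .8c rests on borrowed correlations, and c is unknown. At most about 45 analysed participants per arm contribute, fewer in proportion to uptake. CHAMPS, the co-primary analyses and the secondary outcomes are unaffected by this gap.

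For H3, the supportable statement is conditional: activity summaries could move the CHAMPS contrast in either direction if their effect differs by arm, and leave it unchanged if it does not. A dilution figure would rest wholly on assumptions. This is an inexpensive improvement to an exploratory analysis; it does not threaten the trial's main conclusions.

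**What to change.** **Fitbit baseline.** Issue the device at the initial visit to those who accept it. Designate wear from that visit to session 1 as the baseline, preferably only the days before the group is randomised. Upload it at session 1 in both arms. Name one daily summary variable and a minimum amount of wear, and average over days, because the wait for a group to fill will vary. In the Fitbit mediation model, use change from baseline with baseline as a covariate, or equivalently the on-treatment level adjusted for baseline. Add a Fitbit row to Table 5.

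**H3 sensitivity analysis.** Record Fitbit acceptance before randomisation. Report the CHAMPS treatment effect by site and, within San Diego, by acceptance. A main-effect covariate for acceptance would not suffice, because a differential effect is an interaction. Acceptance is self-selected, so the comparison between acceptors and decliners is descriptive. State also whether wearers are shown summaries during sessions.

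**Cost.** Weekly session uploads are already planned, so this needs wording and a record of dates. Confirm that the device holds data over the wait for a group to form; the plan already relies on storage for up to 21 − 8 = 13 weeks before the last upload. The small downside is that participants with little or no wear before session 1 drop out of this one-site exploratory analysis or add missing data to it.
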